23 peginterferon-alpha 2a (PEGASYS®, Roche), 180 mcg per week administered by subcutaneous
24 injection for a total of 24 weeks. Patients will continue treatment with their previous nucleosi(t)ide
25 analogue regimen during the treatment and follow-up phases of this study.

26 Patients will be seen in the outpatient clinic at weeks 2, 4, 8, 12, and 24, during treatment phase, at
27 12 week intervals thereafter up to 48 weeks post-therapy

28 Compliance will be monitored by medication diaries and counting of the residual vials returned at
29 outpatient visits. The side effects will be monitored regularly at each visit during the treatment phase
30 of the study by symptom questionnaires. Peginterferon alfa-2a will be dose reduced or stopped per
31 the dose reduction and stopping rules for peginterferon alfa-2a. Peginterferon alfa-2a treatment can
32 be restarted if the adverse event resolves and the patient is willing to re-start the medication.

33

34 **On-treatment liver biopsy**

35

1 At day 0, all patients will be readmitted to the NIH Clinical Center to start therapy with peginterferon
2 alfa-2a and to undergo a repeat liver biopsy. Biopsy will be scheduled at 6 hours following the first
3 injection of peginterferon, for the purpose of assessing ISG response pattern following the initial
4 exposure to peginterferon. Liver tissue will also be subjected to routine histopathological grading
5 and staging as well as for immune cell, quantitative viral kinetic and cccDNA epigenetic studies as
6 previously described.

7
8 Since the hypothesis to be tested in this study is that response to treatment peginterferon (i.e. loss of
9 HBeAg and HBsAg or both) is mediated by changes in hepatocyte gene transcription profile, it is
10 necessary to obtain liver tissue at two time points-before and 6 hours after the first dose of
11 interferon. Performing two liver biopsies within 12 weeks or even as short as 24 hours has been
12 performed in other Liver Disease Branch studies and has not been associated with an increase in the
13 complication rate or lower patient acceptance.

16 **Monitoring**

17 Day 0

- 18
- 19
- 20 1) Brief clinical evaluation
- 21 2) Review patient's eligibility for study
- 22 3) Symptom questionnaire
- 23 4) Visual analogue scale
- 24 5) Fatigue questionnaire (Promise 7)
- 25 6) Chemistry 20 (sodium, chloride, potassium, bicarbonate, calcium, phosphate, magnesium,

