6 predictive factors associated with a favorable response to peginterferon therapy when added on to
7 long-term NUCs treatment, in patients with HBeAg positive and negative chronic HBV infection.

8

9 **Primary end-points**

10

- 11 1) The primary end-point for this study will be the change in level of ISG expression and NK cell
12 responses before and after 1st peginterferon injection in responders versus non-responders
13 to peginterferon add-on therapy.
- 14 2) Proportion of eAg positive patients showing eAg loss with or without seroconversion at end
15 of treatment and 24 and 48 weeks off therapy.
- 16 3) Proportion of eAg positive patients showing sAg loss with or without seroconversion at end
17 of treatment and 24 and 48 weeks off therapy
- 18 4) Proportion of eAg negative patients showing sAg loss with or without seroconversion at at
19 end of treatment and 24 and 48 weeks off therapy

20

21 **Secondary endpoints**

22

- 23 1. Level of qHBsAg decline at treatment week 12, at end of treatment and 24 and 48 weeks off
24 therapy, compared to pretreatment levels in eAg positive and negative patients
- 25 2. Level of qHBeAg decline at treatment week 12, at end of treatment and 24 and 48 weeks off
26 therapy, compared to pretreatment levels in eAg positive and negative patients
- 27 3. Correlation of qHBsAg levels at initial evaluation, week 12,24,36 and 48 with intrahepatic
28 pregenomic and cccDNA concentration before and after initiation of peginterferon in
29 responders versus non-responders to treatment.
- 30 4. Intrahepatic pregenomic and cccDNA concentration before and after starting treatment with
31 peginterferon.
- 32 5. Epigenetic alterations in HBeAg positive and negative patients following first 1st
33 peginterferon injection compared to pretreatment levels as measured by chromatin
34 immunoprecipitation (ChIp) assays

- 1 6. Frequency and functional activity of circulating and liver infiltrating, HBV-specific T-cells,
2 measured before and during treatment in responders versus non-responders to
3 peginterferon add-on therapy.
4

5 DOSE CHANGES 6

7 **Stopping peginterferon therapy:** 8

9 Add-on peginterferon will be discontinued early for any of the following reasons:

- 10 a) **Toxicity**- the dose of peginterferon will be modified or discontinued according to Table 1:
11 Peg-Interferon Alfa-2a Dose Modification Guidelines (see below).
12 b) **Withdrawal of informed consent** (subject's decision to withdraw for any reason.

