 19 necessary for this study. As Tables 2 is a guideline, investigators may modify the dose based on
 20 clinical judgment.

21

22

23

Table 2: Peg-Interferon Alfa-2a Dose Modification Guidelines

Laboratory Value/Clinical Criteria:	Dose Modification:	Additional Instructions:
ANC:		
$\geq 0.75 \times 10^9$ cells/L	Maintain at 180 μ g	
$\geq 0.25 \times 10^9$ to $< 0.75 \times 10^9$ cells/L	Reduce to 135 μ g	
$< 0.25 \times 10^9$ cells/L	All study drugs should be interrupted until ANC values return to more than 1000/mm ³	Reinstitute at 90 μ g and monitor ANC
Platelets:		

$\geq 50 \times 10^9$ cells/L	Maintain at 180 μ g	
$\geq 25 \times 10^9$ to $< 50 \times 10^9$ cells/L	Reduce to 90 μ g	
$< 25 \times 10^9$ cells/L	Discontinue all study drugs if value is confirmed	Treatment should not be reinstated
ALT:		
ALT $> 10 \times$ ULN	Reduce to 135 μ g or interrupt all study drugs if repeated ALT results are $> 10 \times$ ULN	If ALT increases are progressive or there is evidence of hepatic decompensation therapy should be interrupted
New Ocular symptom(s):		
New decrease or loss of vision or other clinical significant ocular sign or symptom	Interrupt all study treatment	Complete eye examination must be performed.
New or Worsening Neuropsychiatric Signs or Symptoms (Including Depression):	Mild No change Evaluate weekly by visit or phone until symptoms improve.	Evaluate weekly (with visit at least every other week). Consider psychiatric consultation if no improvement. If improved and stable for 4 weeks, may resume normal dosing.
Moderate	Reduce dose to 135 μ g	
Severe	Discontinue all study drug treatment	Psychiatric therapy necessary. Treatment should not be reinstated.
Creatinine Clearance (CrCl):		
< 30 mL/min	Reduce to 135 μ g	
Hemodialysis	Reduce to 135 μ g	

1 Source: adapted from Pegasys® package insert.

2

3

STATISTICAL ANALYSIS

Power calculation

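### The hepatic-decompensation stopping rule, read literally, withdraws the NUC that the rest of the plan continues; five Table 2 rows share the loose wording

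*Combined protocol and SAP*

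**What the plan says.** **NUC.** Under Initiation of Treatment: "Patients will continue treatment with their previous nucleosi(t)ide" regimen, through both the treatment and the follow-up phases. The section Stopping NUCs therapy gives two conditions: HBeAg loss in HBeAg-positive patients, and HBsAg loss, each confirmed on two tests at least six months apart. It lists no toxicity, ALT or decompensation condition.

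**Peginterferon.** The section Stopping peginterferon therapy opens: "Add-on peginterferon will be discontinued early for any of the following reasons". Item a sends toxicity to the dose-modification table. Item c lists laboratory and clinical criteria which, once confirmed, require the subject to discontinue treatment. One of these, confirmed hepatic decompensation, carries an extra parenthesis directing that all treatment be stopped. No other bullet in the list has such an addition.

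**Table 2.** Five rows use wording wider than peginterferon:
- ANC below 0.25 × 10⁹/L: "All study drugs should be interrupted until ANC values return to more than" 1000/mm³
- platelets below 25 × 10⁹/L: "Discontinue all study drugs if value is confirmed"
- ALT above 10 × ULN: reduce to 135 µg or "interrupt all study drugs if repeated ALT results are" still above that level; the additional instruction reads "If ALT increases are progressive or there is evidence of hepatic decompensation therapy should be interrupted"
- new ocular symptoms: "Interrupt all study treatment"
- severe neuropsychiatric symptoms: "Discontinue all study drug treatment"

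None of these collective terms is defined.

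**The concern.** The regimen has two components, peginterferon and the patient's existing NUC. A rule that stops everything therefore stops the antiviral as well, and does so in the setting where the patient is sickest. An investigator who follows the decompensation bullet as written breaks two other parts of the protocol; one who follows those other parts ignores the bullet.

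The stake is mainly patient safety. The Background says that stopping NUCs after one year is associated with high relapse rates, and credits potent NUCs with better clinical outcomes. A secondary stake is interpretation. If a patient lost the NUC early, later HBeAg or HBsAg status (primary end-points 2 to 4) would reflect NUC withdrawal as well as peginterferon. The ISG and NK-cell changes around the first injection are measured too early to be affected.

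**Working it through.** No figure in the plan is at issue, so the check sets the provisions side by side.

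1. **Decompensation bullet against the NUC rules.** Item c already says that a confirmed criterion means discontinuing treatment. If the parenthesis on decompensation meant peginterferon only, it would add nothing. Its natural reading is that it goes further, and the only further drug in the regimen is the NUC. Stopping NUCs therapy does not list decompensation, and Initiation of Treatment continues the NUC without exception. The three provisions cannot all be followed as written.

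2. **Table 2 rows against their context.** Five rows use the wider wording. Several points limit them to peginterferon:
   - Item a of Stopping peginterferon therapy places the whole dose-modification table under the peginterferon lead-in. It gives the number as Table 1, but the title is that of Table 2.
   - The toxicity rule under Initiation of Treatment names peginterferon alone.
   - The table's title and introductory sentence concern peginterferon, and its source line cites the Pegasys package insert.
   - Its doses are peginterferon doses in µg, including the 90 µg restart in the ANC row.

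   These points cover the ALT and ocular rows as much as the other three.

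3. **What the context leaves untidy.** Elsewhere the protocol separates the two drugs in words: at week 24 peginterferon stops and the NUC goes on, and in pregnancy peginterferon stops while the oral agent may continue. Table 2 makes no such statement. The ALT row's additional instruction says only that therapy is interrupted for progressive ALT rises or decompensation. It therefore meets the decompensation bullet on the same clinical event, and neither says what happens to the NUC.

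4. **Scale.** The documents give no rate of decompensation, and no rate at which a NUC would be stopped by misreading. One patient in a group of 30 is 1/30 = 3.3 percentage points of that group's response rate. The planned difference of 25 points is 0.25 × 30 = 7.5 patients.

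**The case against.** The strongest reply is that the documents already settle the scope. Item a, the toxicity rule under Initiation of Treatment, the separate NUC-stopping section and the table's title and doses all point to peginterferon. The NUC is the patient's previous regimen, in place for at least 192 weeks, and not something the study starts. Table 2 is labelled a guideline open to clinical judgment, and safety is reviewed weekly.

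For the five Table 2 rows this largely stands. A reader might infer that the plan orders the NUC stopped for five kinds of peginterferon toxicity, or that the ALT and ocular rows escape the peginterferon heading because item c does not repeat them. Item a rules out both inferences.

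A reader might also turn the interferon toxicity rates under Hazards and Discomforts into a count of patients who would lose the NUC. Those rates count toxicity events and not NUC withdrawals, and the ALT rates come from patients without oral antivirals. Nor does the one-year relapse statement measure the effect of a short interruption here: the inclusion criteria themselves accept earlier NUC gaps of up to 8 weeks, provided none fell in the last 48 weeks.

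The reply does not dispose of the decompensation bullet, which goes beyond the peginterferon lead-in under which it sits. The 72-hour confirmation and investigator assessment in item c guard against acting on a wrong finding, but not against stopping the wrong drug. The guideline clause allows dose changes to peginterferon and is silent on the NUC.

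**Conclusion.** The concern holds as a minor patient-safety wording correction. The decompensation bullet in item c conflicts, on its literal reading, with Stopping NUCs therapy and with the instruction to continue the NUC. The five Table 2 rows are loose wording that context resolves in favour of peginterferon alone; they are worth tidying, the ALT row above all.

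The number of patients affected cannot be estimated from the documents and is probably very small. That judgment rests on the contextual safeguards, on the exclusion of decompensated disease at entry, and on the protocol's own expectation that large ALT flares will be rare under combination therapy. The conclusion also assumes that the sponsor means the NUC to continue through decompensation, as the other sections imply.

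**What to change.** - **Item c, decompensation bullet:** replace the parenthesis with *discontinue peginterferon; continue the NUC*.
- **Table 2, the five rows:** replace the collective terms with *peginterferon* and add *continue the NUC unless a NUC stopping condition is met*.
- **Table 2, ALT row, additional instruction:** name peginterferon as the therapy to interrupt, with the same statement about the NUC.
- **Item a:** correct the table number while the section is open.

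The cost is a wording amendment to one table and two lines of text, with no extra visits, tests or patients.

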It is not possible to calculate power for the primary endpoints. We have calculated power for the secondary endpoints of the rates of HBeAg and HBsAg loss. Response rates in patients in both groups will be compared to historical controls of HBeAg positive and negative. It is assumed that if these patients were followed for an additional year without peginterferon, only 10% of the HBeAg positive patients would become HBeAg negative and 5% of the HBeAg negative patients would become HBsAg negative. A sample size of 29 HBeAg positive and 27 HBeAg negative patients will provide the study with a statistical power of 80% to detect a difference of 25% (35% versus 10% for HBeAg loss and 30% versus 5% for HBsAg loss). The sample size was increased to 30 patients in each arm to allow for withdrawals.

Variables to be analyzed in association with a serological response will include: baseline ALT and HBV DNA level, liver histology, HBV genotype, IL28B genotype, duration of NUC therapy, and ISG levels. Patients with missing data or who drop out of the study will be considered as treatment failures on an intention to treat basis. For comparison of means, Student's t-test will be used. All reported p-values will be 2-sided.

Demographics and Baseline Characteristics

The following will be summarized for treated subjects:

- Demographics: age, race, gender, geographic region, ethnicity;
- Disease characteristics at baseline: HBV DNA level, HBV genotype, IL28B SNP genotype and cirrhosis status, duration of NUC therapy;
- Physical measurements at baseline; height, weight, body mass index, hip and waist circumference;
- Laboratory tests at baseline;

Analysis plan

To address the primary hypothesis that ISG levels are related to virological response to peginterferon, the ISG analysis of the on treatment liver biopsy at 6 hours after the first dose of interferon will be correlated with off-peginterferon serological outcome (HBeAg loss/seroconversion and HBsAg loss). To address the hypothesis that ISG levels are related to HBsAg levels, the ISG analysis of the on treatment liver biopsy will be correlated with HBsAg levels at weeks 4, 12, 24.. The

1 analyses will be stratified by HBV genotype and duration of NUC therapy.

2

3 **Analysis methodology**

4

5 The analysis will be based on standard approaches to analysis of microarray data. Since the software
6 and approaches change frequently in this field, we will provide a broad outline of the approach

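### Does counting withdrawals as failures undo the allowance for withdrawals in the sample size?

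*Combined protocol and SAP*

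**What the plan says.** Everything needed is in the Power calculation section under STATISTICAL ANALYSIS.

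- Comparator: "Response rates in patients in both groups will be compared to historical controls of HBeAg positive and negative". The reference rates are fixed assumptions. Without peginterferon, "only 10% of the HBeAg positive patients would become HBeAg negative" over a further year, and the matching figure for HBsAg loss in the HBeAg-negative group is 5%.
- Size: "A sample size of 29 HBeAg positive and 27 HBeAg negative patients will provide the study with a statistical power of 80" per cent, "to detect a difference of 25% (35% versus 10% for HBeAg loss and 30% versus 5% for HBsAg loss".
- Increase: "The sample size was increased to 30 patients in each arm to allow for withdrawals".
- Withdrawals: "Patients with missing data or who drop out of the study will be considered as treatment failures on an intention to treat basis".
- Testing: "All reported p-values will be 2-sided". The only test named in the section is a t-test for means.
- Scope: "It is not possible to calculate power for the primary endpoints", so this is the only power statement in the document.

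The section gives no expected withdrawal rate, no significance level for the calculation and no test for a proportion. It does not say whether 35% and 30% already count withdrawals as failures. The Analysis methodology section says that a more detailed analysis plan will be written before data analysis starts.

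**The concern.** Adding one patient for each expected withdrawal keeps the number of analysed patients at target when withdrawals leave the analysis. Under this plan they do not leave. Each one stays in the denominator as a non-responder, while the 10% and 5% references stay where they are. If 35% is the response rate among patients who complete, 3 withdrawals of 30 turn it into 35% × 27/30 = 31.5%, and the detectable difference shrinks from 25 to 21.5 percentage points. One extra HBeAg-positive patient would not obviously make up for that.

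At stake is how far the only power statement can be trusted. A reader would take 30 per group to mean 80% power after withdrawals, and for HBeAg loss that might not be so.

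**Working it through.** **Inputs.** From the Power calculation section: rates of 35% against 10% and 30% against 5%; 29 and 27 patients; 30 per group enrolled; two-sided p-values; withdrawals counted as failures. Assumed, because not stated: a 5% significance level, and 0 to 6 withdrawals of 30.

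**Step 1: reproduce the plan's sizes.** The one-sample normal formula with the variance taken at the alternative rate is

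n = (1.96 + 0.8416)² × p1(1 − p1) / (p1 − p0)²

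- HBeAg loss: 7.849 × 0.35 × 0.65 / 0.25² = 28.57, rounded up to 29.
- HBsAg loss: 7.849 × 0.30 × 0.70 / 0.25² = 26.37, rounded up to 27.

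Both figures match, so the sizing contains no arithmetic error.

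**Step 2: the same formula at n = 30 with withdrawals as failures.** Replace p1 by p = p1 × (1 − k/30) for k withdrawals. Power = Φ[(p − p0)√30 / √(p(1 − p)) − 1.96].

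| Withdrawals k | HBeAg loss | HBsAg loss |
|---|---|---|
| 0 | 81.9% | 84.8% |
| 1 | 78.8% | 82.6% |
| 2 | 75.4% | 80.1% |
| 3 | 71.7% | 77.5% |

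On this approximation one withdrawal takes HBeAg loss below 80%. But the formula understates the power of the tests that could be run, as the next steps show.

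**Step 3: cut-offs of actual tests at n = 30, two-sided 5%.**

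- HBeAg loss, p0 = 10%: P(X ≥ 8) = 0.0078 and P(X ≥ 7) = 0.0258. An exact test with 2.5% per tail rejects at 8, and so does the Wald test. A two-sided exact test that orders outcomes by probability rejects at 7, because P(X = 0) = 0.0424 exceeds P(X = 7) = 0.0180 and the p-value is therefore 0.0258. The score test also rejects at 7: z = (7/30 − 0.10)/√(0.09/30) = 2.43.
- HBsAg loss, p0 = 5%: P(X ≥ 5) = 0.0156, so both exact versions reject at 5. The Wald test rejects at 6. The score test rejects at 4: z = (4/30 − 0.05)/√(0.0475/30) = 2.09.

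**Step 4: binomial power.** The k withdrawals contribute no responders, so power = P(Bin(30 − k, p1) ≥ cut-off).

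| k | HBeAg, cut-off 8 | HBeAg, cut-off 7 | HBsAg, cut-off 6 | HBsAg, cut-off 5 |
|---|---|---|---|---|
| 0 | 87.6% | 94.1% | 92.3% | 97.0% |
| 1 | 84.9% | 92.6% | 90.7% | 96.2% |
| 2 | 81.8% | 90.8% | 88.7% | 95.3% |
| 3 | 78.2% | 88.5% | 86.4% | 94.1% |
| 5 | 69.4% | 82.7% | 80.7% | 91.0% |
| 6 | 64.3% | 78.9% | 77.1% | 88.9% |

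**Step 5: the withdrawals that the increase covers.** These are 30 − 29 = 1 HBeAg positive and 30 − 27 = 3 HBeAg negative. With them counted as failures, the least favourable cut-offs give 84.9% and 86.4%. Both exceed the stated 80%.

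**The case for a change.** The strongest case for a change is that the formula which reproduces 29 and 27 itself falls below 80% for HBeAg loss at one withdrawal (78.8%), and for HBsAg loss at three (77.5%). By the plan's own method, then, the increase does not hold the target. Withdrawals are also plausible. There are 24 weeks of treatment and 48 weeks of follow-up, the Consent process section excludes patients who refuse either biopsy from further participation, and antigen loss must be confirmed at two visits at least 12 weeks apart. These loss rates also appear in the list of Primary end-points, although the power paragraph calls them secondary. And the unnamed test decides whether three withdrawals matter for HBeAg loss: 78.2% at a cut-off of 8, 88.5% at 7.

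Part of this stands. The withdrawal rate, the test and the status of 35% and 30% are not written down, and a power statement is clearer when they are.

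The rest carries less weight.

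- The sizing formula is a conservative approximation. At n = 30 with no withdrawals it gives 81.9% for HBeAg loss, where even the stricter binomial cut-off gives 87.6%. That reserve absorbs the first two withdrawals.
- The breach at three depends partly on a step in the discrete cut-off. The tail probability at 7 of 30 is 0.0258, just over 0.025. At 29 patients it is 0.0216, and the equal-tailed exact test rejects at 7. With three withdrawals that test has P(Bin(26, 0.35) ≥ 7) = 85.8% power at 29 patients, against 78.2% at 30.
- Adding patients is not the wrong kind of adjustment. It restores power when withdrawals are failures too, but takes more patients to do so. Patients lost before dosing may also leave the denominator, since the plan does not say that they count as failures. For them a one-for-one increase is the right tool.
- Under an intention-to-treat failure rule, 35% and 30% can equally be read as rates that already include withdrawals. Nothing is then lost, and the phrase about withdrawals is merely redundant.

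**Conclusion.** No change follows. The two sentences fit together loosely, but the plan does not miss the 80% that it states. With one HBeAg-positive and three HBeAg-negative withdrawals counted as failures, power is at least 84.9% and 86.4% under the Wald, exact and score cut-offs.

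For HBeAg loss to fall below 80%, two things must hold together. First, 35% must be the rate among patients who stay. Second, at least 3 of 30 must withdraw with a cut-off of 8 (78.2%, a shortfall of 1.8 points), or at least 6 of 30 with a cut-off of 7 (78.9%). HBsAg loss stays at 80.7% or more through five withdrawals under the Wald test, and at 88.9% with six under the exact test.

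These figures rest on an assumed two-sided 5% level and an assumed range of withdrawals, since the document gives neither. What is missing is detail that analysts can supply: the test belongs in the detailed analysis plan already promised, and the rest would only annotate the power statement. Writing it down would leave 30 per group, the failure rule, the analysed data and the conclusions as they are.

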7 rather than detailed, specific steps.

8 a) We will perform quality control and background normalization of the gene array data.

9 b) Expression value estimates will be obtained and quantile normalization and median scaling
10 of the genes will be performed.

11 c) A list of genes up- or down-regulated >2-fold with $p > 0.05$ will be prepared using the
12 following procedure:

- 13 1. For each patient, genes up- or down-regulated >2-fold in the second biopsy
14 compared to the first will be identified.
- 15 2. Lists will be prepared of genes that are up- or down-regulated >2-fold for any of the
16 subjects.
- 17 3. A paired t-test will be used to identify genes from this list that have a p value < 0.05
18 (Difference is not equal to zero).
- 19 4. The subset of the genes in (3) that are up- or down-regulated in >50% of patients in
20 groups defined relapse and/or presence of cirrhosis will be identified.
- 21 5. This procedure will be repeated with $p < 0.01$, but the primary analysis will be
22 based on the genes selected using $p < 0.05$.

23 d) The false discovery rate (FDR) of the t test will be estimated.

24 A more detailed statistical analysis plan will be developed prior to the start of data analysis.

25

26

27

HAZARDS AND DISCOMFORTS

28

The risks and discomforts of frequent phlebotomy.

30 To document stable levels of biochemical and serologic markers of chronic hepatitis and to monitor
31 the effects and toxicities of the combination of peginterferon alfa-2a and the nucleos(t)ide analogue
32 frequent blood sampling will be required. Patients will have between 11 and 12 venipunctures
33 during the study. Each venipuncture will be for approximately 20 to 75 cc of blood. The total amount
34 of blood drawn during an 8 week period will not exceed 10.5 ml/Kg or 550 mls, whichever is smaller.

35

The risks and discomforts of HIV testing.

36

1 Patients will have blood tested for anti-HIV at entry. Mention of anti-HIV is made in the consent form
2 which includes the exact language used in the standard consent form used for anti-HIV testing at the
3 Clinical Center. It is important to test for HIV infection as many of the drugs used to treat hepatitis B
4 (tenofovir, tenofovir and emtricitabine, lamivudine and entecavir) have activity against HIV and a
5 treatment regimen using only two drugs against HIV would not be considered standard of care.

7 **The risks and discomfort of percutaneous liver biopsy.**

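### The only test named for comparing means pools the variance, yet responder and non-responder groups are expected to be unequal in size; Welch's test would be a safer prespecified choice

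*Combined protocol and SAP*

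**What the plan says.** All references are to the combined protocol and SAP.

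- **Statistical Analysis, Power calculation:** "For comparison of means, Student's t-test will be used", followed by "All reported p-values will be 2-sided". Nothing is said about equal variances, and no unequal-variance or rank alternative is offered. The same section counts dropouts and patients with missing data as treatment failures.
- **Primary end-points, item 1:** the change in ISG expression and NK cell "responses before and after 1st peginterferon injection in responders versus non-responders".
- **Secondary endpoints, item 6:** frequency and function of HBV-specific T cells, "measured before and during treatment in responders versus non-responders to" add-on therapy.
- **Analysis plan:** the 6-hour ISG result "will be correlated with off-peginterferon serological outcome (HBeAg loss/seroconversion and HBsAg loss"), stratified by HBV genotype and NUC duration. No test is named.
- **Analysis methodology:** "A paired t-test will be used to identify genes from this list that have a p value < 0.05". This compares the second biopsy with the first in the same patient, not responders with non-responders. The section closes by promising a fuller statistical analysis plan before data analysis starts.

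**The concern.** End-point 1 and secondary end-point 6 compare a continuous measure between two independent groups, and the t-test sentence is the only named method that fits. The pooled test estimates one common variance. With equal group sizes, a wrong common-variance assumption does little harm. With unequal sizes, the larger group dominates the pooled estimate, so the standard error is too small when the smaller group is the more variable one and too large when it is the less variable one.

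Here nothing balances the groups, because membership is decided by outcome. At stake is the p-value for the main mechanistic contrast. It could claim an ISG, NK or T-cell difference too readily, or be needlessly conservative, depending on an SD ratio that nobody knows in advance.

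**Working it through.** **1. The plan's own sample size.** The targets are "35% versus 10% for HBeAg loss and 30% versus 5% for HBsAg loss". The formula n = (1.960 + 0.842)² × p₁(1 − p₁) / (p₁ − p₀)², with (1.960 + 0.842)² = 7.849, gives:

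- HBeAg loss: 7.849 × 0.35 × 0.65 / 0.25² = 28.57, rounded up to 29
- HBsAg loss: 7.849 × 0.30 × 0.70 / 0.25² = 26.37, rounded up to 27

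Both match the stated 29 and 27. The calculation covers response rates against a fixed historical value. It does not cover the responder contrast, for which the plan says power cannot be calculated.

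**2. Group sizes implied by those rates, with 30 enrolled per stratum.**

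- HBeAg positive: 0.35 × 30 = 10.5, so 10–11 v 19–20
- HBeAg negative: 0.30 × 30 = 9, so 9 v 21
- Combined: 10.5 + 9 = 19.5, so about 20 v 40
- At the assumed rates without peginterferon: 0.10 × 30 + 0.05 × 30 = 4.5, so about 5 v 55
- At the 60% HBsAg loss of the small pilot study cited in Background: 0.60 × 60 = 36, so 36 v 24

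**3. The mechanism in figures, 20 v 40, assumed SDs 2 (responders) and 1 (non-responders).**

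- True variance of the difference: 4/20 + 1/40 = 0.225
- Variance the pooled test expects: [(19 × 4 + 39 × 1)/58] × (1/20 + 1/40) = 1.983 × 0.075 = 0.149
- The standard error is understated by √(0.225/0.149) = 1.23
- The critical value 2.002 therefore acts like 2.002/1.23 = 1.63, which a normal variable exceeds two-sided about 10% of the time

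With SDs 0.5 and 1 the variances are 0.0375 and 0.0566. The factor is 0.81, the effective cut-off is 2.46, and the rate is about 1.4%.

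**4. Simulation.** Normal data, equal means, two-sided 0.05, 3,000,000 replicates per cell. Alpha 0.05 is assumed for this contrast, because the plan states none. The SD ratio (responder/non-responder) is also assumed, because the documents give no SDs. Entries are rejection rates of the pooled test; the last column is Welch's test across the same ratios.

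| Split (responders v non-responders) | Ratio 0.5 | 1 | 1.5 | 2 | Welch |
|---|---|---|---|---|---|
| 20 v 40 | 1.8% | 5.0% | 8.5% | 11.2% | 5.0% |
| 11 v 19 | 2.4% | 5.0% | 7.8% | 9.9% | 5.0–5.1% |
| 10 v 20 | 1.9% | 5.0% | 8.6% | 11.4% | 4.9–5.1% |
| 9 v 21 | 1.5% | 5.0% | 9.4% | 13.0% | 4.9–5.2% |
| 36 v 24 | 8.4% | 5.0% | 3.5% | 2.8% | 5.0% |
| 5 v 55 | 0.1% | 5.0% | 16.0% | 26.2% | 5.3–5.8% |
| 3 v 27 | 0.2% | 5.0% | 15.5% | 25.4% | 6.6–7.6% |

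The first four rows are the planned case. The 36 v 24 row shows the direction reversing once responders are the majority. The last two rows are the case of no treatment effect, overall and in the HBeAg-positive stratum (0.10 × 30 = 3). There the pooled test is at its worst, but Welch's test also drifts above 5%.

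**The case against.** The strongest reply is that the error depends on a quantity the documents do not contain. No SD is given for ISG, NK or T-cell change, and at ratio 1 the pooled test is exact. The Background remark that T cells are impaired in chronic infection does not separate responders from non-responders and says nothing about spread. This stands: the point is about robustness to an unknown, not a demonstrated error.

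Second, the link to the primary analysis is partly inferred. The Analysis plan speaks of correlating ISG results with outcome under stratification, the gene selection already uses a paired test, and a fuller analysis plan is promised. A reader might infer that a pooled test is prescribed for every comparison of means, but the documents do not say that, and the words pooled variance do not appear. What remains is that the t-test sentence is the only named method for a two-group contrast, and the correlation wording does not cover the NK or T-cell comparisons. The promised plan is the natural place to settle the matter.

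Third, a reader might infer that the groups are unequal by design. They are not: sizes follow from response, and the imbalance is only what the planning rates lead one to expect. At the pilot's rate the imbalance, and with it the bias, runs the other way.

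Fourth, Welch's test is weakest where the pooled test does worst, with very few responders. This also stands and limits the remedy.

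**Conclusion.** The concern holds as a cheap improvement to the plan, conditional on unequal spread. At the splits implied by the target rates, the pooled test's true level is about 8–9% at an assumed SD ratio of 1.5, 10–13% at ratio 2 and 1.5–2.4% at ratio 0.5. At ratio 1 there is no error. Welch's test stays at 4.9–5.2% over the same range. These figures assume normal data and a two-sided 0.05 level.

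A reader might infer an error of two to five times the nominal level. The documents do not support that as a general statement. At planned rates, a ratio of 1.5 gives 1.6 to 1.9 times and a ratio of 2 gives 2.0 to 2.6 times. About five times needs a doubled responder SD together with response no better than the rate assumed without peginterferon. Nor does it follow that the p-value will be wrong whatever happens, since that requires the variances to differ.

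**What to change.** In the Power calculation section, or in the promised fuller analysis plan, replace the t-test sentence with wording such as: between-group comparisons of means, including responders versus non-responders, will use Welch's unequal-variance t-test with a 95% confidence interval for the difference; within-patient change will use the paired t-test. Add that if either group has about five patients or fewer, the comparison is descriptive, because Welch's test is then also unreliable (about 7% at 3 v 27). State as well whether this test, or some other, is what correlating ISG with outcome means.

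The change is one or two sentences and needs no extra data. If the variances are in fact equal, Welch's test costs a little power:

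- 20 v 40, difference 0.8 SD: 81.2% against 81.9%
- 9 v 21, difference about 1.1 SD: 73% against 76%
- 5 v 55, difference about 1.3 SD: about 60% against 78%, a real loss, but in a setting to be treated as descriptive

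If responders are less variable (ratio 0.5, 20 v 40, difference 0.8 non-responder SD), Welch's test gains power: 98% against 95%.
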